1.2. Methodological aspects

medical product of interest Not applicable
First ethics committee to evaluate the study: Autonomous CEIm of Galicia
Principal Investigators / Coordinators [REDACTED] [REDACTED]

[REDACTED]
 
[REDACTED]
 
[REDACTED]

Researcher/Coordinator Centers:
 
¹ Valencian Institute of Oncology
 
² San Carlos Clinical Hospital of Madrid
 
³ Puerta del Hierro-Majadahonda University Hospital
 
⁴ Lucus Augusti University Hospital, Lugo

Autonomous Communities of Researchers / Coordinators:
 
Valencian Community
 
Autonomous Community of Madrid
 
Galicia

Territorial scope:
 
National, Spain

Information source:
 
Medical records of the patients included after signing informed consent.
 
RETROSPECTIVE PART ONLY: medical records of patients included after signing informed consent or waiver thereof in the cases contemplated (see 6.3 Informed consent).

Type of study (according to the AEMPS classification):
 
EPA-AS

Tracking Type::
 
Ambispective (Prospective and retrospective). A 6-month follow-up is proposed for patients in the prospective part.

Total number of patients expected to include:
 
They are expected to include 250, sufficient to respond to the objectives set by the study.

Planned duration of the study:
 
Data collection 8 months. The estimated duration of the project is 12 to 18 months, depending on the patient inclusion rate.

Study duration for each participant:
 
No specific study visits will be carried out, other than obtaining informed consent in cases where it is required.

Main objectives:
 
a) Main objectives
 
i) Describe the population infected by COVID-19 with genitourinary tumors (urothelial cancer, prostate cancer, testicular cancer and renal cancer) treated in Spanish hospitals, know the clinical presentation, therapeutic evolution and

- prognosis of said intercurrent infectious process, as well as its possible relationship with different clinical and therapeutic factors.
- ii) Assess the possible relationship of the different oncological treatments administered to these patients with the clinical evolution of COVID-19 infection, considering both patients who have undergone oncological treatment previously, during or after COVID-19 infection.

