3.2. Secondary objectives

- To evaluate the mortality associated with COVID-19 infection in the population with genitourinary tumors. Percentage of patients alive/dead at discharge.
- To evaluate the rate (percentage) of complications that have required hospital admission and/or ICU treatment.
- Describe the frequency of asymptomatic or minimally symptomatic COVID-19 infections. Percentage of asymptomatic patients or with mild symptoms included in the study.
- Evolution of the oncological disease. Impact/influence of COVID-19 infection on the effectiveness of oncological treatment. Data will be collected on delays/modifications in follow-up or oncological treatment regimens. The average delay time and the number of modifications will be evaluated. Likewise, it is expected to obtain data on time to progression and overall survival of cancer patients, which can be compared with the reference values for each type of tumor pathology.

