5. VARIABLES

5.1. Study variables

A data collection notebook will be prepared in which the following variables will be collected for analysis:

Affiliation of the center:

- Hospital name
- Province
- Investigator's name
- Patient number

Patient characteristics:

- Age
- Sex
- Age
- Hospital center where the patient is recruited (in order to have epidemiological data on the pandemic that may be of interest)

Pathological history:

- Concomitant pathology (cardiac, pulmonary, renal, liver, Diabetes Mellitus, HIV, AI)
- Usual pharmacological treatment
- Smoking and alcohol habit

Tumor pathology:

- Tumor type, histology and stage (initial and at diagnosis of infection)
- Date of cancer diagnosis
- Active cancer treatment or follow-up
- Participation in clinical trial
- Type of treatment most recently received for the infection (Surgery; Radiotherapy; Chemotherapy: Drug, Immunotherapy, TD: Drug, HT: ADT alone or with Abiraterone, Enzalutamide, others)
- Treatment lines
- Start and last dose received of the most recent oncological treatment

For patients with prostate cancer:

- Local treatment and type (Surgery, Radiotherapy)
- Adjuvant ADT or advanced disease (start date)
- NAH (date and line of treatment)
- Associated corticosteroid treatment: Prednisone vs Dexamethasone (dose)

COVID-19 infection data:

- Confirmation date of COVID-19 infection
- PCR diagnostic test
- IgG or IgM serological diagnostic test
- Present symptoms

- Analytical alterations, lymphopenia, elevated CRP, high D-dimer.
- Thrombosis associated with COVID-19 infection
- Date of onset and disappearance of symptoms
- Days duration of fever and cough
- Radiological examination at the moment of greatest severity
- Complications of infection: presence of complications and/or hospital or ICU admission
- Admission date
- Date of most serious complication
- Treatments received for COVID-19
- Discharge status
- Fecha de alta / exit
- Negativization of the presence of viruses by PCR
- Negative PCR date

For patients who are receiving or have received immunotherapy treatments, additional information will be collected:

- Immunotherapy treatment line
- Start/end date of immunotherapy treatment
- Date of last dose received prior to COVID-19 infection
- Immunotherapy received as monotherapy or combination
- Type of immunotherapy
- Adverse effects

Prospective follow-up data (6 months from patient inclusion):

- Date of start or restart of oncological treatment after infection

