- Negative COVID-19 test prior to starting/restarting treatment
- Change/suspension of oncological treatment after COVID-19
- Surgery date in neoadjuvant patients
- Recurrence of COVID-19
- Best answer obtained
- Date of progression to oncological treatment
- Current status
- Last contact date

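### Average treatment delay leaves out interrupted patients who die, stop for good or have not restarted by last contact; report time to restart with death as a competing event

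*Combined protocol and SAP*

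**What the plan says.** Section 3.2 (Secondary objectives) covers delays and modifications in oncological treatment and follow-up, and gives the summary: "The average delay time and the number of modifications will be evaluated". It does not define who is eligible for a delay, when the delay starts or when it ends.

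Section 5.1 (Study variables) lists what could be used:

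- A possible start: "Start and last dose received of the most recent oncological treatment", or the confirmation date of the infection. No planned date for the next dose is listed.
- The end: "Date of start or restart of oncological treatment after infection". It appears only in the block that begins "Prospective follow-up data (6 months from patient inclusion". A surgery date for neoadjuvant patients could do the same job in that subgroup, but it too exists only if the event occurs.
- For non-restart: "Change/suspension of oncological treatment after COVID-19", with no date attached, plus current status and "Last contact date".

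Section 1.2 adds: "A 6-month follow-up is proposed for patients in the prospective part". It states no follow-up for the retrospective part. It also gives "Data collection 8 months".

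Section 4.5 plans a descriptive analysis of each variable and names Kaplan-Meier and log-rank methods for survival only. Section 6.3 expects many deaths and waives consent for certain deceased patients so that they are not lost from the sample.

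**The concern.** A plain average needs a number from every patient. A patient whose treatment was interrupted and never resumed within follow-up has no number, so the average is taken over those who did resume. The patients left out include those whose treatment was disrupted most. The study takes care to keep deceased patients in the sample, yet this summary would drop any of them who died before restarting.

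At stake is the reading of one descriptive result. A short average delay could mean that treatment resumed quickly, or that slow and absent restarts were not counted. The mean alone cannot tell these apart.

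**Working it through.** **No figure to reproduce.** The documents give no expected delay, restart rate or death rate. The 250 patients in section 4.5 are an expected number without inputs. Everything below rests on stated assumptions, shown over a range.

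**Step 1: late restart only.** Let the time to restart be exponential with true mean m months, and let only restarts up to 6 months be seen. The mean among those seen is

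E[T | T ≤ 6] = (m − (6 + m)·e^(−6/m)) / (1 − e^(−6/m)).

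For m = 2: (2 − 8 × 0.0498) / 0.9502 = 1.69 months. The understatement is 1 − 1.69/2 = 16%.

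| True mean (months) | Restarted by 6 months | Mean among them | Understatement |
|---|---|---|---|
| 1 | 99.8% | 0.99 | 1% |
| 2 | 95.0% | 1.69 | 16% |
| 3 | 86.5% | 2.06 | 31% |
| 4 | 77.7% | 2.28 | 43% |

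The percentage depends only on the ratio of window to mean. A 3-month window with a true mean of 2 months has ratio 1.5, as does 6/4, and so also gives 43%. The window matters because it may be shorter than 6 months for some patients. If the 8 months of data collection contain both inclusion and follow-up, only those included in the first 8 − 6 = 2 months can have the full 6.

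**Step 2: add death and permanent stops.** Simulation of 1,000,000 interrupted patients per scenario, with independent exponential death (10–30% by 6 months), a fraction who never restart (0–20%) and a true mean of 1–3 months among the rest. The comparator is the mean time alive without treatment within 6 months, over all patients.

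| True mean | Dead by 6 months | Never restart | With a delay value | Mean, restarters | Mean untreated time, all |
|---|---|---|---|---|---|
| 1 | 10% | 0% | 98.1% | 0.97 | 0.98 |
| 2 | 20% | 10% | 80.4% | 1.61 | 2.15 |
| 3 | 10% | 0% | 83.4% | 2.02 | 2.50 |
| 3 | 10% | 20% | 66.8% | 2.02 | 3.14 |
| 3 | 30% | 20% | 61.4% | 1.92 | 2.86 |

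The restarters' mean was the lower figure in every scenario, by about 0.01 month up to 3.14 − 2.02 = 1.12 months. In the second row, the median time to restart with death as a competing event is 1.69 months, against 1.22 among restarters only.

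**Step 3: what drives it.** Raising the never-restart fraction from 0% to 20% leaves the restarters' mean at 2.02: the mean does not register permanent stops at all. Raising deaths from 10% to 30% moves it only from 2.02 to 1.92. The untreated time over all patients also falls with more deaths (3.14 to 2.86), so no single mean carries restart and death together.

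**The case against.** The strongest reply is that nothing is hidden. Mortality, overall survival and the number of modifications are in the same set of objectives, and a permanent suspension can count as a modification. Read beside these, a mean among restarters is a legitimate description. This stands, provided that the mean is labelled and the number without a value is shown. The plan does not ask for either.

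Second, if most interrupted patients restart within about a month, the bias is negligible. That also stands, but it cannot be known in advance.

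Third, 6 months from infection is a simplification. Follow-up runs from inclusion, so a patient infected earlier and then followed is observed for longer after infection, and the loss is smaller. For late inclusions the window may be shorter.

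Fourth, a patient treated without interruption has zero delay and needs no restart date, and patients off treatment at infection have nothing to interrupt. If uninterrupted patients are also left out, the average over all treated patients moves up. The downward direction is therefore a statement about interrupted patients.

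A reader might infer more than the documents support:

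- That the plan excludes these patients. It does not say so; the exclusion follows from the listed variables and the absence of a rule.
- That comparisons of delay between treatments will be biased. The generic tests in section 4.5 would permit such a comparison, but none is specifically planned.
- That deaths and permanent stops account for the understatement in the first table. That table is truncation alone.
- That every date for a better analysis is already collected. The suspension item has no date.

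**Conclusion.** The point holds for patients on active treatment whose treatment was interrupted. The planned average is biased low for restarts after the end of observation. For deaths and permanent stops it is undefined: their delay has no end, and understatement there means only relative to time spent without treatment.

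The size is conditional: about 1% to 43% for true means of 1 to 4 months, assuming exponential restart and a 6-month cut-off from the start of the interruption. None of these inputs comes from the documents. With deaths and permanent stops added, 61–98% of interrupted patients would have a value, under assumed true means of 1 to 3 months. This is a descriptive item within one secondary objective, so it does not threaten the study, but the wording should be changed before analysis.

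**What to change.** Change the wording in section 3.2 and add a short analysis rule in section 4.5:

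1. Define the denominator as patients on active treatment at infection, a status the variable list already records. Count those with no interruption as zero delay and report how many there are.
2. For those interrupted, make the main summary the cumulative incidence of restart from COVID-19 confirmation (or from last dose; choose one), with death as a competing event and censoring at last contact.
3. Keep permanently suspended patients in the denominator as not restarted, since without a suspension date they cannot be given an event time.
4. Report the proportions restarted, dead and not restarted at fixed times such as 1, 3 and 6 months, and the median if reached.
5. A mean among restarters may be kept if labelled as such, with the number of patients behind it.

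The cost is one reworded objective and one standard analysis. There are three downsides. A curve is less simple to quote than a mean. The quantity becomes time to restart and not delay against schedule, because no planned next-dose date is collected. The sponsor must also confirm that the date of death can be derived from current status and last contact date, and that a blank restart date can be read as either uninterrupted or not restarted.

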4.5. Study sample size

The inclusion of a total of 250 patients with genitourinary tumors presenting with COVID-19 infection is expected, sufficient to respond to the objectives set by the study.

Given the characteristics of the study, the total number of patients cannot be previously calculated accurately, although the inclusion of approximately 250 patients is expected. The planned analysis is the descriptive one of each of the variables. The qualitative variables will be compared with each other using the Chi-square test. Quantitative and qualitative analysis using Student's T analysis or ANOVA. If necessary, the corresponding non-parametric tests will be applied. Survival will be calculated using Kaplan-Meyer curves and curve comparison using Log-Rank.

The Statistical Package for the Social Sciences (SPSS) will be used for statistical analyses. Additional analyzes could be performed with other statistical analysis packages.

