4.9. Study schedule

Study start date (Activation of the first center)	3Q 2020
End date of the study (“Last patient last visit” or end of data extraction)	1T 2021
Study report completion date	2T 2021
Date of first publication	2Q 2021 (expected)

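### The promised comparison of time to progression and overall survival with reference values has no defined time origin and is not supported by 6 months of prospective follow-up with ordinary Kaplan-Meier

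*Combined protocol and SAP*

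**What the plan says.** The last secondary objective, in 3.2 and repeated in 1.2, concerns the effect of COVID-19 on the effectiveness of cancer treatment. It ends by stating, separately by tumour type, that "it is expected to obtain data on time to progression and overall survival of cancer patients, which can be compared with the reference values". No reference source, time point or method for the comparison is given.

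On follow-up, 1.2 describes the design as "Ambispective (Prospective and retrospective") and adds: "A 6-month follow-up is proposed for patients in the prospective part". Section 5.1 heads the relevant block of variables "Prospective follow-up data (6 months from patient inclusion"). Progression date, current status and date of last contact are listed in that block and nowhere else. Outside it, the listed outcomes are status and date at discharge. No length of follow-up is given for the retrospective part.

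Section 5.1 also collects the date of cancer diagnosis, the start of the most recent treatment, and the start or restart of treatment after infection. Any of these could serve as a time origin, but none is named as one. The whole survival method is one sentence in 4.5: "Survival will be calculated using Kaplan-Meyer curves and curve comparison using Log-Rank".

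**The concern.** A survival time can be set beside a published value only if both are counted from the same starting point and the study observes the part of the curve on which the published value lies. The plan secures neither.

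If time runs from inclusion, prospective patients contribute at most 6 months, so a longer median cannot be read off the curve. If time runs from diagnosis or treatment start, the axis is longer, but 4.3 admits patients infected before, during or after treatment. Many therefore enter part-way through their cancer course, having had to survive to do so. Ordinary Kaplan-Meier treats that earlier time as time at risk.

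At stake is a statement about whether COVID-19 impairs cancer control. The first choice gives no median to compare. The second makes outcomes look better than they are. Neither answers the objective.

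**Working it through.** **The plan's own figure.** The sample size of 250 comes with no alpha, power, effect size or event rate, so there is nothing to reproduce. Descriptively, it gives a 95% CI half-width of 1.96 × √(0.25/250) = 6.2 points for a proportion of 50%.

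**Inputs.** Follow-up of 6 months from inclusion (1.2, 5.1) and 250 patients (4.5). Three things are assumed, because the documents do not give them: reference medians m, exponential times, and an equal split over four tumour types (250/4 = 62.5, taken as 63).

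**Clock at inclusion, everyone followed for the full 6 months.**
- Event-free at 6 months: S(6) = 0.5^(6/m).
- Expected events: n × (1 − S(6)).
- Chance that the Kaplan-Meier median is reached: the binomial probability of at least n/2 events (rounded up) with event probability 1 − S(6).
- 95% half-width of S(6): 1.96 × √(S(6)(1 − S(6))/n).

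| Assumed median (months) | S(6) | Events, n = 63 | Median reached, n = 63 | Median reached, n = 250 | Half-width, n = 63 |
|---|---|---|---|---|---|
| 6 | 50.0% | 31.5 | 0.50 | 0.53 | ±12.3 points |
| 9 | 63.0% | 23.3 | 0.018 | <0.0001 | ±11.9 points |
| 12 | 70.7% | 18.5 | 0.0003 | <0.0001 | ±11.2 points |
| 24 | 84.1% | 10.0 | about 0 | about 0 | ±9.0 points |
| 36 | 89.1% | 6.9 | about 0 | about 0 | ±7.7 points |

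For m = 12: 0.5^(6/12) = 0.707; 63 × 0.293 = 18.5; 1.96 × √(0.707 × 0.293/63) = 0.112.

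**The calendar may shorten this.** Section 1.2 states "Data collection 8 months". The schedule in 4.9 runs from 3Q 2020 ("Activation of the first center") to the first quarter of 2021 (last visit "or end of data extraction"), which is 3.1 to 9.0 months. If inclusion were uniform over 8 months with a common cut-off (assumed), only patients included in the first 2 months, or 2/8 = 25%, could complete 6 months. Mean follow-up would be 0.25 × 6 + 0.75 × 3 = 3.75 months. Early censoring on this scale means that 6-month results need Kaplan-Meier estimates, not raw proportions.

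**Clock at treatment start, ordinary Kaplan-Meier.** Take a true median of 12 months and suppose, for illustration, that every patient enters 6 months after treatment start and is then watched for 6 months. No event can be recorded in the first 6 months, so the curve stays at 100% until then. At 12 months it reads 0.5^(6/12) = 70.7%, where the true value is 0.5^(12/12) = 50%. The direction does not depend on the entry time chosen: time survived in order to enter is counted as time at risk, so the estimate is too high.

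**The case against.** The strongest reply is that longer times are not out of reach. The dates needed for an earlier origin are collected, and patients enter at different points of their course. Delayed-entry Kaplan-Meier can then piece together a curve well beyond 6 months although each patient is observed for only 6. Simulation supports this (500 runs, exponential times, entry uniform over twice the median, 6 months observed). For a true median of 24 months and n = 250, the median was estimable in every run, typically about 24 months, with 95% of estimates between roughly 15 and 36. With 63 patients the spread is far wider, about 11 to 46 months, and sensitive to how few patients are at risk soon after the origin. This stands, so a reader should not conclude that medians beyond 6 months are unmeasurable in principle. But 4.5 does not plan the method, and its precision per tumour type is poor.

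Three further readings are tempting, and the documents do not support them.
- That follow-up stops at 6 months for everyone. The limit is stated for the prospective part only. Retrospective follow-up is undefined. From the pandemic declaration on 11 March 2020 (section 2.2) to the first quarter of 2021 is 9.7 to 12.6 months. Under 6.3, retrospective patients who died before authorization can be included under a consent waiver, so their time from infection can include deaths.
- That a mean truncated at 6 months will be set beside a reference median. No section plans this.
- That most of the cohort will yield no result. This rests on assumed reference medians and an assumed tumour mix.

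It is also fair to say that the objective speaks of reference values, not medians, is worded permissively, and belongs to a study that 6.1 calls descriptive. A 6-month rate is a legitimate reference value. Under the exponential assumption, power against a hazard ratio of 1.5 (one-sample, two-sided 5%) is 97% and 82% with n = 250 for reference medians of 12 and 24 months, but 50% and 35% with n = 63. The rate must still share its origin with the reference. A 6-month proportion from inclusion, in patients who enter mid-course, does not match one counted from treatment start.

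**Conclusion.** The concern holds in a limited form. Followed as written, the plan gives either unreached medians (clock at inclusion, reference median clearly above 6 months) or upward-biased curves (clock at diagnosis or treatment start, ordinary Kaplan-Meier). This goes beyond missing detail, because neither route delivers the comparison that objective iv announces.

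The sizes rest on assumed exponential medians and, per tumour type, an assumed equal split. The limit at inclusion applies to the prospective part, and for references at or below about 6 months it may not bite. It would be wrong to say that no comparison is possible: one at 6 months with a matching origin is, and so in principle is delayed-entry estimation of longer medians. This is a secondary objective and should be corrected before analysis. It does not threaten the main descriptive aims.

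**What to change.** In 3.2, 1.2 and 4.5:
- Define the time origin for time to progression and for overall survival.
- State the length of follow-up and the outcome variables for the retrospective part (with a matching entry in 5.1), and reconcile the 6-month follow-up with the 8-month data collection and the 4.9 schedule.
- Limit the external comparison to Kaplan-Meier estimates of survival and progression-free status at 6 months, with 95% CIs, by tumour type and setting.
- Name the reference source, and compare only with a 6-month rate that uses the same origin, for example in patients who start a treatment after infection.
- Where the origin precedes inclusion, use delayed-entry (left-truncated) Kaplan-Meier.
- Do not compare a median with a reference unless it is reached within observed follow-up or estimated with delayed entry. Otherwise report both endpoints descriptively.

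For the prospective part this is wording and method only, using dates already planned. For the retrospective part it may mean recording existing outcome fields for those patients too. The price is a more modest claim with modest precision per tumour type: about ±9 to ±11 points at an assumed 63 patients and reference medians of 24 and 12 months. That precision should be stated in the plan.

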4.3. Inclusion criteria

- Patients ≥18 years old.
- Diagnosed with genitourinary cancer (urothelial, kidney, prostate and germ cell).
- COVID-19 infection prior to oncological treatment, during treatment or after treatment.
- COVID-19 infection must be confirmed by PCR or serology, regardless of whether or not the patient requires hospitalization due to the infection. Additionally, clinical and/or radiological determination must be available in those patients who present symptoms.

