4.4. Exclusion criteria

- Not applicable.

As this study is an EPA-AS, all the researchers' activities are carried out in accordance with the center's usual clinical practice. No withdrawal criteria have been established. Information from the clinical history will be collected as long as it does not exist on the part of the researcher, patient refusal to do so. Therefore, those patients who do not attend the corresponding visits will be declared as lost to follow-up, those patients who withdraw their consent to participate, the data collected up to that point will be used for statistical analysis, being lost to follow-up from which the patient withdraws his consent.

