4.7. Case definition

A "case" is defined as any patient, diagnosed, treated or followed up at the different hospital centers where physicians authorized by the sponsor are informed, who meets the inclusion criteria.

Medical care will be provided following applicable clinical criteria, in the context of routine clinical practice, regardless of the patient's inclusion in the study and following the best judgment of the specialists responsible for the patients.

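### Time to progression and survival are to be set against reference values by tumour type alone, in a cohort mixing follow-up-only, localised and advanced patients, so a difference cannot be read as an effect of COVID-19

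*Combined protocol and SAP*

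**What the plan says.** Section 3.2, last secondary objective (item iv in the section 1.2 summary), asks how COVID-19 affects the effectiveness of cancer treatment. It covers delays and modifications, both in follow-up and in treatment regimens. It then expects data on "time to progression and overall survival of cancer patients, which can be compared with the reference values for each type of tumor pathology". The unit is all cancer patients and the only stratum named is tumour type.

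Eligibility is broad. Section 4.3 requires "Diagnosed with genitourinary cancer (urothelial, kidney, prostate and germ cell") and accepts "COVID-19 infection prior to oncological treatment, during treatment or after treatment". Section 4.4 answers the exclusion criteria with "Not applicable". Section 4.7 counts as a case "any patient, diagnosed, treated or followed up at the different hospital centers" that meets the inclusion criteria.

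Section 5.1 shows that a mixed cohort is expected and that the mix will be recorded: "Active cancer treatment or follow-up" and "Tumor type, histology and stage (initial and at diagnosis of infection"), together with treatment type and line. The outcome fields for the six-month prospective follow-up include treatment change or suspension, best response, "Date of progression to oncological treatment", current status and last contact date.

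Section 4.5 gives the methods: description, chi-square, t-test or ANOVA, Kaplan-Meier and log-rank. It gives no analysis set, time origin or stratification for this objective, no source for the reference values and no method for comparing with them.

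**The concern.** Within one tumour type, prognosis differs greatly between a patient disease-free after local treatment and a patient on a later line for metastatic disease. A curve that pools them is an average weighted by whatever mix the centres happen to enrol. A published reference value has its own mix. The gap between the two combines the COVID-19 effect with the difference in mix, and nothing in the plan separates them.

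The protocol applies this standard to others. Section 2.2.3 faults one cancer cohort for possibly mixing cured and metastatic patients, and another for leaving differing stages out of its multivariate model. The comparison in 3.2 leaves the same gap open.

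A related gap concerns denominators. Treatment change, best response and progression on treatment have no defined value for a patient who is not on treatment and does not start it. The plan does not say which patients count for each measure.

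**Working it through.** **1. The plan's own figure.** The only relevant figure is the expected 250 patients (4.2, 4.5). No error rate, power, effect size, event rate or precision stands behind it, so there is nothing to reproduce. The documents give neither the share of follow-up-only patients nor any reference value. What follows illustrates the mechanism; it does not estimate the bias.

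**2. Inputs.** From the documents: a six-month horizon (5.1) and 250 patients. Assumed: exponential times; median time to progression of 8 months in treated active disease (range 6 to 12) and 60 months in follow-up only (range 60 to 120); a true COVID-19 hazard ratio r of 1.0 or 1.5 among treated patients and none in follow-up-only patients; a follow-up-only share f of 20%, 40% or 60%.

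**3. Reference made up of treated patients only.**
- Reference, progression-free at six months: 2^(−6/8) = 0.595.
- Treated study patients at r = 1.5: 2^(−1.5×6/8) = 0.459.
- Follow-up only: 2^(−6/60) = 0.933.
- Pooled: S = (1−f)×S_treated + f×0.933.
- Apparent ratio: ln S / ln 0.595.

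Example for f = 20%, r = 1.5: S = 0.8×0.459 + 0.2×0.933 = 0.553, and the ratio is 0.592/0.520 = 1.14.

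| f | Progressed at 6 months, r = 1.0 | Apparent ratio | Progressed at 6 months, r = 1.5 | Apparent ratio |
|---|---|---|---|---|
| 0% | 40.5% | 1.00 | 54.1% | 1.50 |
| 20% | 33.8% | 0.79 | 44.7% | 1.14 |
| 40% | 27.0% | 0.61 | 35.2% | 0.83 |
| 60% | 20.2% | 0.43 | 25.7% | 0.57 |

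Over the assumed ranges of the medians, the ratios for r = 1.5 are 1.07–1.19, 0.74–0.91 and 0.47–0.65 at f = 20%, 40% and 60%.

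**4. Reference that contains more low-risk patients than the study.** Let 40% of the reference and 20% of the study be follow-up only.
- Reference: 0.6×0.595 + 0.4×0.933 = 0.730, with −ln = 0.315.
- Study, r = 1.5: S = 0.553, ratio 0.592/0.315 = 1.88.
- Study, r = 1.0: S = 0.8×0.595 + 0.2×0.933 = 0.662, ratio 0.412/0.315 = 1.31.

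So the sign of the bias changes with the reference population.

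**5. Matching the overall mix is not enough.** With 40% follow-up only in both, a true 1.5 among treated patients reads as 1.38. Comparing treated patients with a treated reference gives 1.5 (row f = 0%).

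**6. Precision cost of restricting the denominator.** The half-width is 1.96×√(0.5×0.5/n) for an assumed 50% rate: 6.2 points at n = 250, 6.9 at 200, 8.0 at 150 and 9.8 at 100, that is, with 0%, 20%, 40% and 60% not applicable.

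**The case against.** The best defence is that the plan is silent here rather than wrong. The comparison is worded permissively, section 4.5 describes the planned analysis as descriptive, and stage and treatment status are collected, so an analyst could stratify. One can add that Tumor pathology is also the heading in 5.1 that covers stage and treatment status, so the wording of 3.2 might be meant more broadly than tumour type. This stands in part. It limits the point to a clarification of a secondary objective. It does not make the comparison interpretable as written, and if finer strata are intended, saying so is most of the fix.

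Three stronger readings are tempting, and the documents support none of them.

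- A reader might infer that follow-up-only patients will be scored as having no modification and no progression. No section says so. The resulting dilution (an assumed 50% modification rate falling to 40%, 30% or 20% at f = 20%, 40% or 60%) would arise only if they were kept in the denominator.
- A reader might infer that these patients cannot be assessed on this objective at all. Survival can be assessed for everyone through current status and last contact date. Section 3.2 expressly includes changes to follow-up, although 5.1 lists no variable for them. Patients infected before treatment become assessable once they start it.
- A reader might infer that pooling makes COVID-19 look less harmful. That needs a reference population of treated or advanced disease, which the plan does not name; step 4 of the working shows the reverse.

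Nor does the 64.3% in stages I–III cited in section 2.2.3 supply the missing share. It comes from 28 patients, 3 of them with genitourinary cancer, and stage I–III does not mean off treatment.

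**Conclusion.** The point holds as a cheap improvement. Eligibility and the single named stratum together mean that, read literally, the comparison in 3.2 mixes patients with very different prognoses, and a difference from a reference value cannot be attributed to COVID-19 in either direction. This follows from the text alone. The size does not: every ratio in the working rests on assumed medians, shares and hazard ratios, and the documents allow no estimate. The numbers show only that plausible differences in mix can hide, reverse or exaggerate an effect of ordinary size. The lack of denominators for the treatment-dependent measures is missing detail, not a stated error.

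**What to change.** In 3.2 and 4.5, add a few sentences:

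1. Report time to progression and overall survival within tumour type by stage at infection and treatment setting (follow-up only, localised or adjuvant, advanced). Compare only with named reference values matched on setting. Where no match exists, label the comparison descriptive and do not attribute differences to COVID-19.
2. Restrict treatment modification, best response and progression on treatment to patients who are on treatment at infection or start it afterwards, with that number as denominator. Limiting this to patients on treatment at infection would wrongly drop those infected before treatment, who are eligible and whose start date is collected.
3. For follow-up-only patients, report overall survival, cancer recurrence and any follow-up delays separately.

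Items 1 and 2 use variables already in 5.1. For item 3, the only recurrence field listed there is for COVID-19 and no follow-up delay is listed, so these two may each need a field unless the current-status entry covers recurrence. No extra patients are needed.

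The cost is smaller strata and wider intervals: 8.0 instead of 6.2 points for an assumed 50% rate if 40% of 250 are not applicable. Intervals will be wider still within tumour type and setting, and for six-month outcomes, which only the prospective patients supply; their number is not stated. Sparse strata should be described without testing.
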